4.1. Treatment Misallocations

In order to assess treatment misallocations, drug dosing information will be collected. Treatment misallocations will be handled as follows. If a participant is:

- Randomized but not treated (i.e. if the participant has a randomization number but no treatment or PK data), then the participant will be excluded from all the statistical analyses.
- Randomized but took incorrect treatment, then the participant will be reported under his/her randomized group for all efficacy analyses. The participant will be reported for safety and Pharmacokinetic (PK) analysis under his/her actual randomized arm.
- Participants randomized to the incorrect stratum at baseline will be allocated to the correct stratum for analyses using SCR2 biopsy eligibility results collected in the study.
- Treated but not randomized, then by definition the participant will be excluded from the
 efficacy analyses since randomized arm is missing, but will be reported under the dosing
 regimen they actually received for all safety and PK analyses.

Note: Participants randomized to either of the 2 QD dosing regimens of DGAT2i will be analyzed according to the corresponding BID dosing regimen of DGAT2i alone (maintaining the same total daily dose). If a participant has been re-screened then they will only be counted once in all summaries under the original unique SSID#. Information collected on the Demography page of the CRF can be used to determine any previous participant ID that a participant may have been screened under *in this study*.

5. GENERAL METHODOLOGY AND CONVENTIONS

The study will be analyzed and reported once all randomized participants have completed the study (or discontinued), and following study-level data set release.

5.2. General Methods

For the assessment of dose-response, the following BID treatment groups (at a minimum) will be included in a Bayesian E_{max} dose-response model:

- Placebo
- DGAT2i 25 mg BID
- DGAT2i 75 mg BID including those randomized to 150 mg QD
- DGAT2i 150 mg BID including those randomized to 300 mg QD
- DGAT2i 300 mg BID

Other treatment groups will be analyzed to assess the comparisons as shown below:

- DGAT2i 150 mg BID + ACCi 5 mg BID vs Placebo and vs DGAT2i 150 mg BID
- DGAT2i 300 mg BID + ACCi 10 mg BID vs Placebo and vs DGAT2i 300 mg BID

5.2.1. Analyses for Binary Endpoints

Dose Response Analyses

For binary (responder) endpoints in the study, to be analyzed under a composite estimand strategy all cases of withdrawal from treatment for lack of efficacy or toleration or if a Week 48 biopsy is not performed will be considered to be non-responders. Such endpoints will be analyzed by fitting a Bayesian E_{max} dose-response model. This model will be utilized to characterize the dose response across all BID treatment groups, to estimate the proportion of responders (and 90% credible interval) for each BID dose studied, and to estimate the placebo-adjusted proportion of responders for each dose (and 90% credible interval). If the E_{max} dose-response model cannot be fitted to the data, then other models that allow dose

response to be estimated will be fitted, ie, linear, log-linear or exponential. No adjustment for multiple comparisons will be made.

The 3 parameter Emax model will be fitted to the response at Week 48 on placebo and all DGAT2i monotherapy BID doses – the actual dose to be modelled should be the Total Daily Dose (i.e. BID dose*2). If the model converges, model estimated parameters will be presented along with their 90% credible intervals. The model projected placebo adjusted treatment effect for each BID dose (i.e. Total Daily Dose) will also be presented along with their credible intervals.

The Bayesian estimation of the Emax model uses prior distributions on the placebo response (E0), dose that produces half maximal drug effect (ED₅₀) and Emax parameters. The specification of the Emax model and the prior distributions for some of its parameters are based on three meta-analyses of clinical dose response from more than 100 compounds (Thomas, 2014; Thomas & Roy, 2017; Wu, 2017).

The DGAT2i ED₅₀ for the histological-based primary endpoint has been assumed to be slightly higher than the projected EC₅₀ for reduction in liver fat which was estimated from a preliminary population pharmacokinetic model based on previous clinical studies with DGAT2i. Therefore, the DGAT2i ED₅₀ was estimated to be approximately 30 mg BID (TDD = 60 mg). The substantial uncertainty in ED₅₀ values was assessed in the meta-analyses of clinical dose response studies (Thomas, 2014). Therefore, based on the meta-analyses, a scaled t-distribution (with 5 degrees of freedom) is planned to be used that is focused on the initial projected ED₅₀=30 mg BID, with a scale parameter of 0.6. A normal prior distribution for the logit of the placebo response centered at logit(0.16) with a prior standard deviation of 2.0 (logistic scale) is planned to be used, which yields a weak diffuse prior distribution for the placebo response. A normal prior distribution for the Emax parameter will also be used, centred on the anticipated Emax (0.6) on the logistic scale. This prior distribution will also be diffuse on the logistic scale with a prior standard deviation of 2.0.

The proportion of primary endpoint responders in each treatment group will be analyzed by fitting a Bayesian Emax model to the data to characterize the dose response across all treatment groups and to estimate the proportion of responders (and 90% credible interval) for each dose studied, and to estimate the placebo-adjusted proportion of responders for each dose (and 90% credible interval). If an Emax model cannot be fitted to the data, then other models that allow dose response to be estimated will be fitted, i.e. linear, log-linear or exponential.

Note that a similar methodology will be used for the exploratory 'worsening from baseline' liver biopsy endpoints, but for this Estimand 3.1 will be utilized.

Pairwise Treatment Comparisons

The comparison of the proportion of responders for binary responder endpoints for DGAT2i BID doses vs placebo, and DGAT2i+ACCi BID doses vs placebo and corresponding DGAT2i BID monotherapy doses will be analyzed using logistic regression models, including baseline (SCR2 Eligibility) fibrosis stage (F2/F3) as a factor, to estimate the

proportion of responders in each treatment group and odds ratio and risk difference (and corresponding 90% CIs) for each treatment comparison. Risk difference and 2-sided 90% confidence interval for risk difference will be calculated by using the observed placebo rate and estimated odds ratio from the logistic regression model. For comparisons of DGAT2i+ACCi BID doses vs corresponding DGAT2i BID monotherapy doses corresponding 50% CI will also be provided. No adjustment for multiple comparisons will be made.

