2.3.2. Benefit Assessment

The current study is the first time that DGAT2i and DGAT2i + ACCi is being administered to the target population – ie, those with biopsy-confirmed NASH and liver fibrosis stage of F2 or F3, as assessed by sponsor-identified central pathologist(s). For the participants of this study, close monitoring of their medical condition and safety will occur as outlined in this protocol. In the Original Protocol, for every 9 participants randomized, 8 who receive

DGAT2i or DGAT2i + ACCi may potentially derive benefit from the desired pharmacology, namely, reversal of hepatic steatosis, decrease in hepatic inflammation and improvement in hepatic fibrosis. Following implementation of Protocol Amendment 1, for every 7 participants randomized, 6 who receive DGAT2i or DGAT2i + ACCi may potentially derive benefit. Those randomized to placebo (1 in every 9 [Original Protocol] or 1 in every 7 [Protocol Amendment 1] participants) are not expected to obtain any specific benefit, beyond close monitoring of their medical condition and safety. All participants will receive general, standard-of-care guidance/counseling regarding the overall benefits of diet/exercise.

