in Imaging Substudy to offer dedicated consent for this procedure closer to Baseline MRI-PDFF or at the time of consent obtained at SCR1). Population identified to be considered for PreQ will include those with common conditions identified as risk factors associated with NAFLD. 16 In addition, eligible population identified to be overweight, obese, as well as morbidly obese though upper limit of acceptable BMI capped at 45 kg/m². Between the PreQ and SCR1 visits, many of the non-invasive procedures and clinical laboratory tests assessed are identical – this is motivated by the intent to confirm that the population progressed to liver biopsy at SCR2 is consistently characterized. As a measure of additional diligence and as an attempt to remove variability due to differences from laboratory-to-laboratory, the clinical laboratory tests assessed at PreQ and SCR1 are proposed to be analyzed by the sponsor-identified central laboratory. The non-invasive assessments to narrow the population ultimately undergoing screening/baseline liver biopsy consist of double-confirmation between assessment at PreQ and SCR1 of.— (a) blood-based markers of liver function (ie, ALT, AST, alkaline phosphatase, total bilirubin) and ensuring participants have stable results (defined by <50% variability in ALT/AST/alkaline phosphatase¹³ plus total bilirubin <ULN, unless Gilbert's syndrome); (b) consistent presence of concomitant risk factors associated with NAFLD; and (c) evaluation of FASTTM score¹² (a composite of FibroScan® derived CAPTM and VCTETM plus AST) to identify at-risk participants of progressive NASH. The FASTTM score threshold of ≥0.30 for eligibility was derived using individual-level data co-owned by EchoSens, the manufacturer of FibroScan®, and shared with the sponsor for the purposes of designing this protocol. The threshold of CAPTM ≥280 dB/m plus VCTETM between 8.0 and 20.0 kPa, inclusive, is permitted to account for the limited cases where evaluable FibroScan® results are highly suggestive of presumed NASH with fibrosis 17 but the FASTTM score is below 0.30.

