5.3. Randomization Criteria

A computer-generated randomization code using the method of random permuted blocks will be utilized to randomize participants equally balanced across the 9 study interventions (Original Protocol) or the 7 study interventions (Protocol Amendment 1) on Day 1/Visit 5 prior to the first dose of the double-blind, double-dummy study intervention provided participants satisfy all the following criteria:

- Eligibility criteria outlined in Section 5.1 and Section 5.2;
 - Including reconfirming that participants are willingness to undergo the 2nd biopsy, while in the study;

- A negative urine drug test for illicit drugs for sample collected at Visit 4/Baseline, as reported by sponsor-identified central laboratory;
- Fasting (≥8 hours overnight, with water permitted) serum triglyceride result of ≤400 mg/dL (4.5 mmol/L), for sample collected at Visit 4/Baseline, as reported by sponsor-identified central laboratory
 - A single repeat assessment permitted using sponsor-identified central laboratory, though results of this repeat, when done, must be available ahead of randomization;
- Fasting (≥8 hours overnight, with water permitted) plasma glucose result of ≤270 mg/dL (15 mmol/L), for sample collected at Visit 4/Baseline, as reported by sponsor-identified central laboratory
 - A single repeat assessment permitted using sponsor-identified central laboratory, though results of this repeat, when done, must be available ahead of randomization;
- In females, a negative serum pregnancy test result at Visit 4/Baseline, as reported by sponsor-identified central laboratory;
 - Plus, in females of childbearing potential, urine pregnancy test on Day 1/Visit 5, as reported on-site using supplies offered by sponsoridentified central laboratory, are negative for pregnancy – refer to Section 8.2.6;
- In those with hypertension, BP controlled via adjustment of concomitant medications for BP control during the Run-In period with seated BP on Day 1/Visit 5 of <160/100 mmHg;
- Noted to be ≥90% and ≤110% compliant with doses administered (based on tablet count) with the single-blind placebo administered from Visit 4/Baseline to 1 day before Day 1/Visit 5, inclusive – refer to Section 6.4;
- Total score of <8 on the AUDIT questionnaire, as assessed on Day 1/Visit 5.

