5.5. Screen Failures

Screen failures are defined as participants who consent to participate in the clinical study but are not subsequently randomly assigned to study intervention/entered in the study. A minimal set of screen failure information is required to ensure transparent reporting of screen failure participants to meet the CONSORT publishing requirements and to respond to queries from regulatory authorities. Minimal information includes demography, screen failure details, and any SAE.

The limited participants who screen failed, under the Original Protocol exclusively related to the inclusion criterion #3, inclusion criterion #4, and/or inclusion criterion #6, can be re-screened after Health Authority (where applicable) and IRB/EC approvals of Protocol Amendment 1 – if the amended eligibility criteria can be met. *In addition*, in rare cases, participants may be re-screened; however, this is permitted only when, due to logistical/administrative constraints, the maximum period between PreQ and Day 1/Visit 5, of 16 weeks, is exceeded;

- All such cases must be reviewed with a member of the sponsor's Clinical team before
 the given participant is re-consented;
- All PreQ and SCR1 procedures must be repeated under a new 8-digit SSID number;

 Participants must be deemed to meet all the eligibility criteria including histological assessment of NASH with F2 or F3 fibrosis on SCR2 liver biopsy, as assessed by sponsor-identified central pathologist(s).

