2.2. Study Design

The detailed set-up of the study is summarized below -

Figure 1. Study Design

This is a multicenter, multinational, randomized, double-blind, double-dummy, placebo-controlled, parallel-group, evaluation of DGAT2i alone, and DGAT2i+ACCi. Approximately 350 participants (50 per arm) with biopsy confirmed NASH with F2-F3 fibrosis, as assessed by sponsor-identified central pathologist(s), will be randomly assigned to the study intervention to ensure approximately 280 evaluable participants (40 per arm) offer evaluable data for the primary objective.

Participants will be randomized in a balanced ratio, using a computer-generated randomization code, to receive either double-blind, double-dummy placebo, 1 of 4 doses/dosing regimens of DGAT2i alone, or 1 of 2 dose-levels of DGAT2i+ACCi for a treatment duration of up to 48-weeks.

For participants randomized before Protocol Amendment 1 is enacted, those randomized to either of the 2 QD (DGAT2i 150 mg QD and DGAT2i 300 mg QD) dosing regimens of DGAT2i alone will remain in the study but will be switched to the corresponding BID dosing regimen of DGAT2i alone, maintaining the assigned total daily dose and the double-blind, double-dummy design. New randomization to the QD treatment arms will cease, after Health Authority (where applicable) and IRB/EC approvals of Protocol Amendment 1. Therefore, following Protocol Amendment 1, participants will be randomized to one of the following treatment arms:

Placebo

DGAT2i (Ervogastat) BID dose arms (for characterization of dose-response):

- DGAT2i 25 mg BID, total daily dose of 50 mg
- DGAT2i 75 mg BID, total daily dose of 150 mg
- DGAT2i 150 mg BID, total daily dose of 300 mg
- DGAT2i 300 mg BID, total daily dose of 600 mg

DGAT2i (Ervogastat) + ACCi (Clesacostat) coadministration dose arms:

- DGAT2i 150 mg BID + ACCi 5 mg BID
- DGAT2i 300 mg BID + ACCi 10 mg BID

The treatment group labels in programmed outputs will be as follows:

Placebo	PF-5571	PF-5571	PF-5571	PF-5571	PF-5571	PF-5571	Tota1
	25 mg	75 mg	150 mg	150 mg	300 mg	300 mg	
	BID	BID	BID	BID+	BID	BID+	
				PF1304 5		PF1304 10	
				mg BID		mg BID	

Following footnote to be included on all tables: PF5571 = Ervogastat and PF1304 = Clesacostat Note: A 'Total' column is required when summarizing baseline of population randomized

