The 'PF5571 75 mg BID' group will also include those randomized to DGAT2i 150 mg QD and 'PF5571 150 mg BID' group will also include those randomized to DGAT2i 300 mg QD, therefore, there will be no reference to the QD treatment arms in any of the programmed outputs (including dose at onset for AEs and treatment duration – these will only refer to the BID groups as described above).

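### Pooling the once-daily arms ties treatment group to protocol version, and no efficacy model or listed sensitivity analysis accounts for it; any bias is likely small and is cheap to address

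*SAP*

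**What the plan says.** **Allocation.** Protocol 5.3 has participants "equally balanced across the 9 study interventions (Original Protocol) or the 7 study interventions (Protocol Amendment 1"), and Protocol 2.3.2 confirms it for the control arm: "Those randomized to placebo (1 in every 9 [Original Protocol] or 1 in every 7 [Protocol Amendment 1] participants").

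**Pooling.** SAP 5.2 puts 150 mg QD with 75 mg BID, and lists "DGAT2i 150 mg BID including those randomized to 300 mg QD". SAP 2.2 adds that "New randomization to the QD treatment arms will cease, after Health Authority (where applicable) and IRB/EC approvals of Protocol Amendment 1", and that "there will be no reference to the QD treatment arms in any of the programmed outputs".

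**Eligibility.** Protocol 5.5 says that people whose screen failure was "exclusively related to the inclusion criterion #3, inclusion criterion #4, and/or inclusion criterion #6, can be re-screened" under the amended criteria.

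**Models.** In SAP 5.2.1, "The 3 parameter Emax model will be fitted to the response at Week 48 on placebo and all DGAT2i monotherapy BID doses"; its parameters are E0, ED50 and Emax on total daily dose. The pairwise logistic models contain treatment and fibrosis stage. In SAP 5.2.2 the ANCOVA adds the baseline value, and the MMRM also has week and treatment-by-week. The hypothetical biopsy analysis (SAP 5.3) averages over fibrosis stage and T2DM. The Emax sensitivity analyses in SAP 6.1.1.2 are optional and vary only the priors. The subsets in SAP 6.4 are the imaging substudy and T2DM. Protocol version appears in none of these.

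**The concern.** Within each protocol version the randomisation is fair. Across versions the allocation ratio of the groups as analysed changes: the two pooled groups go from double the size of every other arm to equal size. A plain comparison over both versions then compares groups with different mixes of early and late participants. If early and late participants respond differently, part of that difference is counted as treatment effect.

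A version difference is plausible, because entry criteria were changed at the same point. Approvals also arrive by country and site, so version may track region and calendar time.

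At stake are three pairwise contrasts (75 mg against placebo, 150 mg against placebo, and 150+5 mg against 150 mg) and, to a lesser degree, the fitted Emax curve.

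**Working it through.** **1. The plan's own figure.** Inputs from Protocol 9.2: 350 randomised, 50 per arm (350/7), placebo rate 16%, maximum 60%, ED50 30 mg BID. On a logit Emax curve, 150 mg BID reaches 150/(150+30) of the range, which gives 51.5% and a difference of 35.5 points. By normal approximation, P(observed difference > 24 points) = Φ[(0.355 − 0.24)/√(0.16·0.84/n + 0.515·0.485/n)]. This is 88.0% with n = 40 and 90.6% with n = 50, against a stated probability of at least 89%. The same curve is used in step 4.

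**2. Mix of versions.** Let N0 be the number randomised before the amendment. The documents do not state it, so a range is shown.

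- Each of the five unpooled arms: N0/9 early, (350 − N0)/7 late.
- Each pooled group: 2·N0/9 early, (350 − N0)/7 late.

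| N0 | Unpooled: early/total | Pooled: early/total | Gap |
|---|---|---|---|
| 60 | 6.7/48.1 = 13.9% | 13.3/54.8 = 24.3% | 10.5 |
| 115 | 12.8/46.3 = 27.6% | 25.6/59.1 = 43.2% | 15.7 |
| 167 (maximum) | 18.6/44.7 = 41.5% | 37.1/63.3 = 58.7% | 17.2 |

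**3. Pairwise bias = gap × version difference in response.** The version difference is also an assumption.

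| N0 | 5-point difference | 10-point difference |
|---|---|---|
| 60 | 0.5 | 1.0 |
| 115 | 0.8 | 1.6 |

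If early response is lower, 75 and 150 mg look worse against placebo, and 150+5 mg looks better against 150 mg. If it is higher, the signs reverse. For 300+10 mg against 300 mg neither arm is pooled, so the gap is zero.

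**4. Emax contrast, 150 mg BID against placebo.** This is the posterior mode on expected counts with the SAP priors, taking the ED50 prior as on the log scale and the Emax prior as centred at logit(0.6) − logit(0.16) = 2.06. The range covers a shift constant in logits or constant in percentage points.

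| N0 | 5-point difference | 10-point difference |
|---|---|---|
| 60 | 0.2–0.4 | 0.5–0.8 |
| 115 | 0.4–0.6 | 0.7–1.3 |

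**5. Against the 6-point combination effect.** At N0 = 115 the pairwise bias is 0.8/6 = 13% or 1.6/6 = 27% of it. If that effect means both combinations against both matching monotherapy doses, the early shares are 38.3/105.5 = 36.3% and 27.6%. The gap is then 8.8 points and the bias 0.4 or 0.9 points.

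The SAP adds a 50% interval for this comparison. With no true effect and N0 = 115, the log odds ratio for the 150+5 mg pair shifts by ±0.031 or ±0.063 (SE about 0.395). The chance that the interval's lower limit exceeds zero moves from 25% to 22–28% or 20–30%.

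**6. What the remedies do.** These figures come from 1,500 simulated trials at about N0 = 115, except the posterior-mode figures in the second item.

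- Version factor in the 150+5 against 150 mg model, 10-point difference: mean bias falls from +1.65 to +0.06 points (Monte Carlo SE 0.25). With no difference, the SD rises from 9.44 to 9.55 points (1.2%). Root mean squared error goes from 9.45 to 9.56 with no difference, and from 9.67 to 9.59 at 10 points.
- Version shift in E0 of the Emax model, early response 10 points lower: bias at 150 mg becomes −0.01 if the shift is constant in logits. If it is constant in points, −0.59 of −1.29 remains.
- Excluding QD-randomised participants: every arm has N0/9 early and (350 − N0)/7 late, so the gap is zero. This drops 2·N0/9 people (about 26 at N0 = 115). The SD rises from 5.97 to 6.14 for the Emax contrast and from 9.44 to 10.03 for the pair.

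**The case against.** The harm needs a version difference that the documents do not contain. Entry still rests on a central biopsy read with the same NASH and F2/F3 threshold (Protocol 5.1). The FibroScan-only route "is permitted to account for the limited cases where evaluable" results suggest disease despite a low FAST score (Protocol 4.2). If eligibility is the only mechanism, the version difference equals the newly eligible share times their difference in response. With an assumed share of 20%, a 10-point version difference needs those people to respond 50 points differently, and 5 points needs 25. Screening takes 10 to 16 weeks (Protocol 4.1), so people screened under the old criteria may be randomised after the change, which dilutes the contrast. Protocol 9.5 keeps the first safety review at about 115 randomised, which suggests, without proving, that N0 was lower. All of this stands, and it is why the sizes above are illustrations.

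A reader might infer more than the documents support:

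- **That the primary conclusion is in danger.** SAP Table 9 makes Emax the primary method for every monotherapy contrast, and there the bias is 0.2 to 0.6 points at a 5-point difference.
- **That a lower 50% limit above zero is a decision rule.** SAP 5.1 says the intervals are assessed one-sided, but both documents plan no hypothesis tests and no section sets such a criterion. The percentages in step 5 show sensitivity, not an error rate.
- **That the report would hide the imbalance entirely.** Numbers randomised by arm are planned (SAP 6.5.2), and the excess in a pooled group is about N0/9, so N0 can be roughly inferred. SAP 6.5.1 would show some case-mix differences, such as BMI. What is not planned is arm by version, or response by version.

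Pooling by total daily dose was also disclosed and prespecified. That answers a charge of concealment, but it does not adjust for version.

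**Conclusion.** The structural point holds: for any N0 strictly between 0 and 350, the two pooled groups contain proportionally more early participants than every other arm, and nothing in the efficacy plan accounts for it. The consequence is conditional. If response does not differ by version, the bias is zero.

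Under the assumed 5- or 10-point differences and N0 of 60 to 115, the bias stays well below the sampling error: the SD is about 9.4 points for the 150+5 mg pair and 6.0 for the Emax contrast. It is unimportant for the 24-point placebo difference. It is worth removing for 150+5 mg against 150 mg, because there it can be up to about a quarter of the 6-point effect, while 300+10 mg against 300 mg is untouched. The two combination comparisons would otherwise not be equally protected.

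This is a cheap improvement of minor to moderate weight.

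**What to change.** 1. **Pairwise and repeated-measures models (SAP 5.2.1, 5.2.2).** Add protocol version at randomisation as a two-level factor in the logistic, ANCOVA and MMRM models. Define it by the randomisation list used (nine or seven regimens), not by calendar date, because approvals differ by site. The existing conversion to a risk difference can stay, using the version-adjusted odds ratio.
2. **Emax model (SAP 6.1.1.2).** Leave the primary model unchanged. Prespecify a sensitivity run of the primary endpoint that excludes participants randomised to 150 or 300 mg QD, which restores equal allocation within version. A version shift in E0 is an optional second run. State that it removes the bias only in part if the difference is constant in percentage points.
3. **Visibility (SAP 2.2).** Tabulate numbers randomised per arm by version, and amend the sentence that bars reference to the QD arms so that it allows these outputs.

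**Cost.** The adjusted pair has about 1% more SD, with little change in overall error: the gain is removing and exposing a systematic component, not precision. The QD-excluded run is less precise and therefore supportive only. The rest is modest programming on data already held. The pairwise model is part of the primary endpoint analysis for the combinations, so the sponsor should decide whether the added factor is a major change that SAP section 2 would have reflected in a protocol amendment.
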